8.3.2 Secondary Efficacy Analyses

Additional secondary efficacy analyses will be performed to test the effects of treatment group and their interactions on the secondary endpoints of the change from baseline in CAL and BOP at Day 270. For the CAL analysis, the GEE analyses will be performed with the same statistical model as described in the primary PD efficacy analysis but with the change from baseline in CAL of tooth-sites with baseline PD ≥ 6 mm as the dependent

variable. Separate hypotheses will be performed for testing the treatment effects of group 1 versus group 3 (placebo) and group 2 versus group 3 (placebo). As described above, this model will include the baseline smoker status (smoker or non-smoker) by treatment group interaction. For the secondary efficacy analyses of the BOP change from baseline, ANCOVA will be performed with treatment group as the main effect, and covariates for baseline PD, site, patients, smoker status, and the baseline smoker status (smoker or non-smoker) by treatment group interaction. Point estimates and 95% confidence intervals will be presented for the treatment group differences in CAL and BOP change from baseline at Day 270 and by baseline smoker status.

The CAL and BOP secondary analyses described above will be tested hierarchically in the order of: CAL change from baseline at Day 270, and BOP (presented as a whole mouth average percentage) change from baseline at Day 270. The treatment effects for the CAL or BOP change from baseline at the Day 270 Visit will be compared between Treatment Group 1 and Placebo, and between Treatment Group 2 and Placebo. The alpha will be set at 0.025 to allow for the Bonferroni correction for 2 multiple comparisons for secondary endpoints. Since the smoker status by treatment group interaction is acting as a gatekeeper for further inference testing by smoker status, no additional corrections will be made for multiplicity for any additional analyses of the effects of treatment on CAL and BOP by smoker status. These analyses will be performed once all the subjects (excluding those withdrawn) completed their 270-Day Visit.

All primary and secondary analyses performed on the ITT population will be repeated using the per protocol population.

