
Planned Sample Size: The sample size for the study is based on the sample size required to reject the null hypothesis for the primary efficacy endpoint.
 
The number of subjects was estimated based on 2 meta-analysis studies that reviewed 50 and 72 articles respectively (Bonito, 2005) to reach a significant difference in PD reduction at 9 months compared with placebo.
 
Using the normal approximation for sample size determination for 2 independent samples, t-tests, and assuming a PD reduction of 0.5 mm on average (difference in means) with a standard deviation of 0.7 mm, <math>\alpha=0.05</math> (0.025 per comparison), and 85% power, a sample size of 44 per group will be required. The expected dropout rate is 20% based on previous experiments; hence 50 subjects will be enrolled per group. Generalized estimating equations (GEE) analyses will be performed and therefore, the actual power will be between 85 and 90%.

Statistical methods: Analysis of the clinical efficacy data will consist of modeling endpoints, including change from baseline in PD, CAL, BOP, and FMPI, with treatment group as a main effect and adjusting for baseline values of a given endpoint. Post-baseline treatment comparisons will be modeled through a GEE method (with a linear link and exchangeable covariance matrix), adjusting for the baseline value. Methods of analysis for periodontal flora, inflammatory cytokine levels in GCF and in serum, and RBL will be described in separate statistical analysis plans. Results will be considered significant if <math>p < 0.05</math>.

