3. GENERAL ANALYSIS AND REPORTING CONVENTIONS

For continuous endpoints, the summary statistics will generally include number of subjects with data (n), mean, standard deviation, median, minimum and maximum. No preliminary rounding will be performed; rounding will only occur after analysis. To round, the digit to right of last significant digit will be considered: if < 5 then round down, if ≥ 5 then round up. Means and medians will be presented with one more decimal place than the precision of the data. Standard deviations will be presented with two more decimal places than the precision of the data. Percentages will be presented with one decimal place. Minimums and maximums will be presented with the same precision as the original data.

For categorical endpoints, the summary statistics will generally include: number of subjects randomized and/or dosed, number of subjects with data, and the percentage of those with data in each category. Frequency distributions will be presented as appropriate.

Analysis of the clinical efficacy data will consist of modeling endpoints, including change from baseline in PD, CAL, BOP, and FMPI, with treatment group, patients, smoking status, and investigational site as main effects and adjusting for baseline values of a given endpoint. Post-baseline treatment comparisons will be modeled through a GEE method (with a linear link and exchangeable covariance matrix), adjusting for the baseline value. Methods of analysis for periodontal flora, inflammatory cytokine levels in GCF and in serum, and RBL will be described in separate statistical analysis plans.

Hypothesis testing, unless otherwise indicated, will be two-sided. When confidence intervals are presented, they will be two-sided with a confidence coefficient of 95%. Actual P-values will be reported to 3 decimal places if greater than 0.001. If less than 0.001, the value ' <0.001 ' will be reported.

The statistical software, SAS[®] version 9.3 or above, will be used for all summaries and statistical analyses.

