8.3.1 Primary Efficacy Analyses

The generalized estimating equations (GEE) method with a linear link and exchangeable covariance matrix (within subject correlation structure) will be used to estimate the treatment group effects with respect to change from baseline PD at 270 days, adjusted for baseline PD in tooth-sites with baseline PD ≥ 6 mm. The two primary hypotheses to be tested are:

- 1) The change in PD from baseline (PD ≥ 6 mm) (Screening Visit) at the 270 Day Visit differs between the Group 1 (see section 2.4) and Group 3 (placebo) treatments. Point estimates and 95% confidence intervals will be presented for the

treatment group differences in PD change from baseline at Day 270 by baseline smoker status.;

- 2) The change in PD from baseline (PD ≥ 6 mm) (Screening Visit) at the 270 Day Visit differs between the Group 2 (see section 2.4) and Group 3 (placebo) treatments. Point estimates and 95% confidence intervals will be presented for the treatment group differences in PD change from baseline at Day 270 by baseline smoker status.

SAS code for the GEE model is as follows:

```
proc gee data=Day270dataset
  where (base $\geq$ 6 and ITT Set='Y' and paramcd='PDEPTH');
  class subjid trt01a site smoker_status;
  model chg = trt01a base site smoker_status smoker_status*trt01a;
  repeated sub=subjid /type=exch;
  lsmeans trt01a/pdiff;
run;
```

Where:

- 1) The Day270dataset only includes records for Day 270 visit)
- 2) chg = change from baseline of each individual tooth site
- 3) (base \geq 6 and ittf1='Y' and paramcd='PDEPTH'): subsets the dataset to include only PD outcomes, the ITT population, and tooth sites with baseline PD greater or equal to 6mm.
- 4) chg= change in PD from baseline
- 5) trt01a = treatment group
- 6) site=investigator institution rather than tooth site
- 7) base = baseline PD

The 15-, 30-, and 60-Day visits were not included in the primary statistical model since the tooth-sites at the earlier visits may still be healing from the effects of the SRP procedure with possible SRP-related gingival swelling affecting the PD measures.

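### Read as written, the CAL model in SAP 8.3.2 adjusts for baseline PD and not for baseline CAL, contrary to SAP 3

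*SAP*

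**What the plan says.** - **SAP 8.3.2.** For CAL, "the GEE analyses will be performed with the same statistical model as described in the primary PD efficacy analysis". The one stated change is the dependent variable, which becomes CAL change in tooth sites whose baseline PD is at least 6 mm. Each ST266 group is compared with placebo at 0.025, and CAL is tested before BOP.
- **SAP 8.3.1.** The model line is "model chg = trt01a base site smoker_status smoker_status*trt01a", and the notes define "base = baseline PD". The same variable is in the where clause (`base` of 6 or more, PD parameter code). The notes say that this clause "subsets the dataset to include only PD outcomes, the ITT population, and tooth sites with baseline PD greater or equal to 6mm".
- **SAP 3.** Change in PD, CAL, BOP and FMPI is modelled with the listed factors "as main effects and adjusting for baseline values of a given endpoint".
- **Protocol section 2, synopsis, statistical methods.** The same endpoints are modelled "with treatment group as a main effect and adjusting for baseline values of a given endpoint".
- **SAP Table 8-1, footnote a.** This covers PD and CAL. Its list of model terms (treatment, patients, smoking, investigational site) contains no baseline value.

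The SAP prints no code for CAL and names no separate variables for baseline PD and baseline CAL.

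**The concern.** For PD, one variable can properly do two jobs: it picks the deep sites and it is the endpoint's own baseline. For CAL these are two different measurements. Keeping the 8.3.1 model and changing only the response leaves baseline PD as the sole baseline covariate, so the CAL baseline, which is measured at screening under the schedule of assessments, goes unused.

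CAL is formally tested and stands first in the secondary hierarchy, so its precision also bears on whether BOP is reached. A model that the SAP describes in three different ways also leaves a choice to be made at analysis.

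**Working it through.** **Is there a figure to reproduce?** The documents give none for CAL. The only sizing figure is 44 per group for PD (SAP 2.6: difference 0.5 mm, SD 0.7 mm, 0.025 per comparison, 85% power). The normal approximation gives 2 × [0.7 × (2.2414 + 1.0364) / 0.5]² = 42.1, so 43; an exact t calculation gives 85.5% power at 44. The figure holds, and this point does not affect it.

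**Step 1. Baseline covariate for CAL, place by place.**

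| Place | Baseline covariate for CAL |
|---|---|
| SAP 8.3.2 with 8.3.1 | baseline PD |
| SAP 3 | baseline CAL |
| Protocol synopsis | baseline CAL |
| SAP Table 8-1, footnote a | none listed |

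That is three different answers. The BOP sentence in SAP 8.3.2 also names baseline PD as its covariate, so that section does not follow the own-baseline rule elsewhere either. This favours the literal reading.

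**Step 2. Can one `base` variable serve CAL?**

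- Keep `base` as baseline PD: the sites are right, but baseline CAL is absent, against SAP 3.
- Switch the parameter so that `base` becomes baseline CAL: the covariate is right, but the filter now selects CAL of 6 mm or more. A site with PD 6 mm and CAL 4 mm would drop out. A site with PD 5 mm and CAL 6 mm would come in.

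Neither use satisfies both SAP 3 and the site set in SAP 8.3.2. How many sites the switch would change is unknown. A simulation on assumed distributions used site PD of mean 4.0 mm, rounded down, with SD 0.6 between and 1.5 within patients, and CAL minus PD of mean −0.5 to 1.5 mm and SD 0.7 to 1.5 mm. It lost 0.2% to 42% of the intended sites, and 16% to 76% of the selected sites had PD below 6 mm. The width of these ranges shows only that the documents do not fix the answer.

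**Step 3. Precision.** Let r be the patient-level partial correlation between baseline CAL and CAL change, given baseline PD. This is an assumption, since the documents report no such value. Adding baseline CAL multiplies the residual variance by 1 − r²:

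| r | 1 − r² | Variance reduction |
|---|---|---|
| 0 | 1.00 | 0% |
| 0.2 | 0.96 | 4% |
| 0.3 | 0.91 | 9% |
| 0.4 | 0.84 | 16% |
| 0.5 | 0.75 | 25% |

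Each entry is a ceiling for its r. The model uses a site-level covariate in an exchangeable GEE, where a single slope mixes within-patient and between-patient relations. The full 1 − r² gain on patient means requires that slope to equal the between-patient slope.

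**The case against.** The strongest reply is that SAP 3 already settles the matter. It names CAL and requires "adjusting for baseline values of a given endpoint". On that view, reusing the model means reusing its structure, and the definition of `base` is merely a note to the PD code. SAP 8.3.4 supports this template reading, because it sends FMPI, a 0 to 5 plaque score, to the 8.3.1 method, where a cut at 6 could not apply. This has force: a careful programmer might well adjust for baseline CAL. But that requires overriding an explicit definition, and SAP 8.3.2 itself names baseline PD for BOP. The text therefore does not lead to one model.

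Three stronger readings are tempting, and the documents do not support them:

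- **That the plan analyses the wrong sites for CAL.** It does not. SAP 2.2, Table 8-1, SAP 8.3.2 and Protocol 7.1 all define the set by baseline PD of 6 mm or more. The wrong set arises only if the PD code is reused with the parameter switched, which is a coding risk.
- **That leaving out baseline CAL biases the result.** Treatment is randomised, so on average it does not.
- **That the loss equals a definite number of patients.** One could compute 50/0.96 − 50, about 2, up to 50/0.75 − 50, about 17, per arm of 50. Those values rest on assumed patient-mean correlations that start above zero and do not carry over directly to a site-level GEE covariate. Protocol 11.1 also builds CAL partly from probing depth, so baseline PD may already carry much of the information.

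**Conclusion.** The point holds as a contradiction over the covariate for a formally tested secondary endpoint. Following SAP 8.3.2 as written gives a CAL model without baseline CAL, which SAP 3 and the protocol synopsis call for, while Table 8-1 footnote a names no baseline at all.

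The consequences are some loss of precision, chance imbalance in baseline CAL left uncorrected, and an analyst choice left open. The size cannot be derived from the documents. On an assumed patient-level partial correlation of 0 to 0.5 beyond baseline PD, the variance reduction forgone is 0% to at most 25%. The contradiction itself does not depend on that range. The primary endpoint, the sample size and the alpha allocation are unaffected.

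**What to change.** In SAP 8.3.2, print the CAL model separately with two variables:

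- select sites on `base_PD` of 6 mm or more;
- adjust CAL change for site-level `base_CAL`, with `base_PD` optional as an additional covariate.

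The 0% to 25% range above describes adding baseline CAL to a model that keeps baseline PD. If `base_PD` is dropped, the gain could be smaller. Then add the baseline term to Table 8-1 footnote a so that it agrees with SAP 3.

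The cost is to carry baseline PD onto the CAL records, edit the filter and model lines, and add a sentence of text. Both measurements are already collected. The change should be made before database lock.

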
Planned Sample Size:
 
The sample size for the study is based on the sample size required to compare treatment with ST266 versus placebo for the primary efficacy endpoint.
 
The number of subjects was estimated based on two meta-analysis studies that reviewed 50 and 72 articles respectively (Bonito, 2005).
 
Using the normal approximation for sample size determination for an independent sample t-test, and assuming a PD reduction of 0.5 mm on average (difference in means) with a standard deviation of 0.7 mm, $\alpha=0.05$ (0.025 per comparison, Bonferroni correction), and 85% power, a sample size of 44 per group will be required. The expected dropout rate is approximately 10% based on previous experiments; hence 50 subjects will be enrolled per group.

Statistical methods:
 
Analysis of the clinical efficacy data will consist of modeling endpoints, including change from

baseline in PD, CAL, BOP, and FMPI, with treatment group, smoking status, and investigational site as main effects and the interaction of smoking status and treatment group. Post-baseline treatment comparisons will be modeled through a GEE method (with a linear link and within-patient exchangeable covariance matrix), adjusting for the baseline value. Methods of analysis for periodontal flora, inflammatory cytokine levels in GCF and in serum, and RBL will be described in separate statistical analysis plans.

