8.2 Efficacy Variables

Table 8-1 Efficacy Variables and Analysis Methods

Efficacy Variables	Method 1^a
Primary	
Pocket Depth	Δ from baseline at Day 270 in tooth-sites with baseline PD ≥ 6 mm ^a
Secondary	
Clinical Attachment Level	Δ from baseline at Day 270 in tooth-sites with baseline PD ≥ 6 mm ^a
Bleeding on Probing	Δ from baseline at Day 270 using whole mouth average percentage of site with bleeding on probing ^b

^a Generalized Estimating Equations will be used as the primary analytical method. The dependent variable will be change from baseline to Day 270 and the model will include treatment group, patients, smoking status, and investigational site for a given endpoint. A linear link and exchangeable covariance matrix will be employed. Only treatment comparisons at Day 270 will report a p-value. Comparisons at other time points will only present the point estimate and 95% confidence interval. The analyses will incorporate all data from individual tooth sites within each subject.

^b ANCOVA will be used for the analysis of this variable. The dependent variable will be change from baseline to Day 270 and the model will include treatment group, patients, smoking status, and investigational site for this endpoint. Only treatment comparisons at Day 270 will report a p-value. Comparisons at other time points will only present the point estimate and 95% confidence interval.

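### The SAP gives conflicting baseline covariates for the secondary BOP analysis, and its model descriptions also carry a redundant patient term and a GEE/ANCOVA mismatch

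*SAP*

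**What the plan says.** **Endpoint.** SAP 2.2 defines BOP as one whole-mouth percentage of bleeding sites per patient. Protocol 7.1, SAP Table 8-1 and SAP 8.3.2 agree. The efficacy criteria in the SAP 2 synopsis can be read as limiting BOP to pockets of at least 6 mm at baseline.

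**Baseline covariate for BOP.**
- SAP 8.3.2, the endpoint-specific section: ANCOVA with treatment as main effect "and covariates for baseline PD, site, patients, smoker status", plus the smoker-by-treatment interaction.
- SAP 3, which lists PD, CAL, BOP and FMPI together: change from baseline is modeled "with treatment group, patients, smoking status, and investigational site as main effects and adjusting for baseline values of a given endpoint".
- Protocol Synopsis, Statistical methods, for the same four endpoints: "with treatment group as a main effect and adjusting for baseline values of a given endpoint". Protocol 13 refers to baseline adjustment without more detail.
- SAP Table 8-1, footnote b: "the model will include treatment group, patients, smoking status, and investigational site for this endpoint". It names no baseline and no interaction.

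**Patient term.** It is listed for BOP in 8.3.2 and footnote b, and for the GEE endpoints in footnote a: "the model will include treatment group, patients, smoking status, and investigational site for a given endpoint". The only code in the SAP, for the primary GEE in 8.3.1, has "model chg = trt01a base site smoker_status smoker_status*trt01a" and "repeated sub=subjid /type=exch". The statistical methods paragraph of SAP 2 has "with treatment group, smoking status, and investigational site as main effects and the interaction of smoking status and treatment group", with no patient term.

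**Method.** SAP 2 and SAP 3 put BOP among the endpoints compared by GEE. Footnote b and 8.3.2 specify ANCOVA. No ANCOVA code is given.

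**The concern.** BOP is formally tested: it follows CAL in the hierarchy, with two comparisons against placebo at 0.025 each. Two programmers working faithfully from this SAP could fit different models, one with baseline PD and one with baseline BOP, and report different estimates and p-values. Nothing in the SAP says which text governs. SAP 8.3.2 also does not say which patient-level summary of baseline PD is meant (all sites, or only those of at least 6 mm).

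The patient term raises a separate question, because taken literally it makes the listed model unusable for an endpoint with one record per patient.

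**Working it through.** **The plan's own figure.** SAP 2.6 gives 44 per group, for PD only (difference 0.5 mm, SD 0.7 mm, two-sided 0.025, 85% power). The normal approximation is 2 × [0.7 × (2.2414 + 1.0364) / 0.5]² = 42.1, so 43. The noncentral t version gives 44 (power 0.846 at 43, 0.855 at 44). No BOP effect, SD or covariate enters, so nothing below changes it. The documents state no power for BOP.

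**Design matrix for the BOP ANCOVA.** Inputs: 150 patients and 3 arms (SAP 2.6, 2.5), 6 sites (SAP 2), 2 smoker strata, one baseline covariate, smoker-by-treatment interaction, one row per patient (SAP 2.2).

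1. *No patient term.* Rank = 1 (intercept) + 2 (treatment) + 1 (baseline) + 5 (site) + 1 (smoker) + 2 (interaction) = 12. Residual df = 150 − 12 = 138, and the treatment contrasts are estimable. With the 5 to 7 sites of the Protocol Synopsis, residual df are 139 to 137. The count is the same whether the baseline is PD or BOP.
2. *Patient as a fixed factor.* Rank 150 on 150 rows, so 0 residual df. Neither the Group 1 nor the Group 2 contrast with placebo is estimable.
3. *Patient as a random effect.* With one row per patient, its variance cannot be separated from the residual. On simulated data the REML log-likelihood was the same (−76.997) whether the patient share of a fixed total variance was 0, 25, 50, 75 or 100%. The contrast is the one from step 1.
4. *Several rows per patient, fixed patient factor.* With 6 rows each (900 rows), rank is 151 and residual df 749, but the contrast is still not estimable because patients are nested in treatment. So the term cannot be a fixed main effect in SAP 3 or footnote a either.

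**Which baseline.** Let k be the SD of baseline BOP divided by the SD of Day 270 BOP, r their correlation, and a the correlation of baseline PD with baseline BOP. Suppose that PD acts only through baseline BOP. The residual variance of change adjusted for PD, relative to that adjusted for baseline BOP, is then

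1 + (k − r)²(1 − a²)/(1 − r²).

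The documents give none of k, r or a. On assumed values only:
- k = r = 0.5: ratio 1.00, no gain.
- k = 1, r = 0.5, a = 0.3: 1 + 0.25 × 0.91/0.75 = 1.30, SE 12% lower with baseline BOP.
- k = 1, r = 0.3, a = 0: 1 + 0.49/0.91 = 1.54, SE 19% lower.

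This shows direction only. It does not estimate the gain in this trial.

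**The case against.** **The patient term is loose wording.** The same word appears in footnote a, yet the 8.3.1 code for that model uses the patient only as the GEE cluster, and SAP 2 lists no patient term. A fixed patient factor would fail visibly when run, and a random one changes nothing. This stands. A reader might infer that the planned BOP test cannot be carried out or would yield a wrong result; the documents do not support that.

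**Specific text governs general text.** SAP 8.3.2 is the BOP section and names baseline PD, while SAP 3 and the Protocol Synopsis speak of four endpoints at once. CAL in 8.3.2 reuses the primary model, whose coded baseline is PD, so baseline PD may be deliberate for both secondary endpoints. This stands in part: keeping baseline PD and amending SAP 3 would also remove the contradiction. But SAP 3 and the Protocol Synopsis name BOP expressly and point to its own baseline, footnote b is silent, and no order of precedence is stated.

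**Baseline PD is a legitimate covariate.** This stands. A reader might infer that adjusting BOP for baseline PD biases the treatment comparison. Under randomization it does not.

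**Dropout does not erode the residual df.** A reader might subtract the expected dropouts from 138. For the ITT analysis, SAP 8.1.1 carries each withdrawn patient's worst values to Day 270, so the rows should stay near 150.

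**Conclusion.** The SAP should be corrected here, chiefly because it answers the choice of BOP baseline covariate in more than one way. That choice can change the reported result of a formally tested secondary endpoint. Baseline BOP is the better resolution: two of the conflicting texts already call for it, and it can add precision and correct chance imbalance at baseline. That preference rests on efficiency, not validity, and its size cannot be established from the documents.

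The patient term and the assignment of BOP to both GEE and ANCOVA are secondary drafting faults. The df result for a fixed patient factor rests only on there being one BOP value per patient; it does not depend on site sizes or the share of smokers. That premise follows SAP 2.2, Table 8-1, 8.3.2 and Protocol 7.1 over the ambiguous synopsis line. The primary PD analysis as coded is not affected.

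**What to change.** Before database lock and Day 270 unblinding:

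- In SAP 8.3.2, specify the BOP analysis as an ANCOVA of Day 270 change in whole-mouth BOP percentage on treatment, baseline whole-mouth BOP percentage, site, smoker status and smoker-by-treatment interaction.
- Delete the patient term from 8.3.2 and Table 8-1 footnote b. For consistency, delete it also from SAP 3 and footnote a, where the patient is only the GEE cluster.
- Align footnote b with the full model, including the baseline and the interaction.
- Amend SAP 2 (Statistical methods) and SAP 3 so that BOP is not assigned to GEE.
- Align the BOP wording in the SAP 2 efficacy criteria with the whole-mouth definition in 2.2.

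Because SAP 2.5 has one statistician and one programmer unblinded at Day 90, the team kept blinded should settle the wording.

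Cost: SAP text and one covariate in the BOP program. Baseline BOP is already collected at screening (Protocol Table 3), so no new data are needed, and no planned term other than baseline PD and the patient term leaves the model.

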2.5 Treatment Group Assignments or Randomization

Randomization will be stratified by site and smoker status (never smoked or quit smoking more than two years ago versus has smoked within the last two years). Randomization will be blocked such that assignment to treatment groups both within sites and within

smoker status will be approximately even (1:1:1). ST266 will be supplied to the study site and prepared for use by trained clinical staff, who will not be the same as the dental professionals evaluating the subjects.

At the 90-Day analysis, one statistician and one programmer will be unblinded in order to generate the unblinded 90-day analysis. Another team of statisticians and programmers will remain blinded until the 270-day analysis at the end of the study.

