Since there are two primary hypotheses, Bonferroni corrections will control for multiplicity with $p < 0.025$ considered significant. Point estimates and 95% confidence intervals will be presented for the treatment group differences in change from baseline at each assessment time point. These analyses will be performed once all the subjects (excluding those withdrawn) have been unblinded and completed their 270-Day Visit.

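### CAL and BOP are tested at their own 0.025 per arm with no stated dependence on the PD result, so CAL could be declared significant in an arm where PD failed

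*SAP*

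**What the plan says.** **Primary (SAP 8.3.1).** Two hypotheses on Day 270 PD change are tested, Group 1 against placebo and Group 2 against placebo: "Since there are two primary hypotheses, Bonferroni corrections will control for multiplicity with $p < 0.025$ considered significant".

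**Secondary (SAP 8.3.2).** CAL and BOP "will be tested hierarchically in the order of: CAL change from baseline at Day 270, and BOP". The arms "will be compared between Treatment Group 1 and Placebo, and between Treatment Group 2 and Placebo", and the level is given as follows: "The alpha will be set at 0.025 to allow for the Bonferroni correction for 2 multiple comparisons for secondary endpoints".

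**Gatekeeping.** The only gatekeeper the SAP names is the smoker-by-treatment interaction in 8.3.2. It governs further tests by smoker status, not the step from PD to CAL.

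**Protocol.** Section 7.2 splits 0.05 into 0.025 for each of the two primary comparisons. Section 13 gives a general significance threshold of 0.05. Neither section orders the secondary endpoints or ties them to the primary.

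**The concern.** The SAP has chosen formal error control: a Bonferroni split, an ordered list and a named gatekeeper. A reader will take a result from that scheme to be a protected one. But the ordered list begins at CAL rather than PD and carries its own 0.05 (two comparisons at 0.025). A regimen could therefore miss on PD, and its CAL result could still be reported as significant under a pre-specified, Bonferroni-corrected hierarchy. That label suggests more protection than the scheme gives once PD and CAL are read together.

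The tests of PD themselves are not affected. What is at stake is how a positive CAL result beside a negative PD result may be described.

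**Working it through.** **Inputs**
- Level: 0.025 for each PD comparison (SAP 8.3.1) and 0.025 for each arm comparison on the secondary endpoints (SAP 8.3.2).
- Sidedness: "Hypothesis testing, unless otherwise indicated, will be two-sided" (SAP section 3). The critical value is therefore |z| > 2.241.
- Allocation: treatment assignment within sites and "smoker status will be approximately even (1:1:1") (SAP 2.5). With equal groups and one shared placebo arm, the two arm-versus-placebo statistics correlate at 0.5.
- Correlation r between the PD and CAL test statistics: not in the documents, so **assumed** and varied from 0 to 1.

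**Step 1: the SAP's own level.** Primary pair: 2 × 0.025 = 0.05, as stated. With the shared placebo arm, the exact bivariate-normal chance of at least one false PD finding is 4.65%.

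**Step 2: PD and CAL together, upper bound.** Four tests at 0.025 give at most 4 × 0.025 = 0.10. If all four were independent, the chance would be 1 − (1 − 0.025)^4 = 9.6%.

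**Step 3: PD and CAL together, by correlation.** Simulation with no effect of either arm on either endpoint (3 to 4 million draws per value of r), counting a finding in either direction:

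| r | Any false PD or CAL finding | False CAL finding in an arm where PD failed |
|---|---|---|
| 0 | 9.1% | 4.5% |
| 0.5 | 8.5% | 4.0% |
| 0.7 | 7.9% | 3.4% |
| 0.8 | 7.4% | 2.9% |
| 0.9 | 6.7% | 2.2% |
| 0.95 | 6.1% | 1.6% |
| 1 | 4.65% | 0 |

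BOP adds nothing to the middle column, because it is reached only after a CAL finding, which in this setting is already false.

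**Step 4: which r is plausible.** Protocol 11.1 builds CAL from probing depth and the distance from gingival margin to cemento-enamel junction. As an illustration, suppose the change in margin position is independent of the change in PD and has k times its standard deviation. Then r = 1/√(1 + k²):
- k = 0.5: r = 0.89, combined chance 6.7%
- k = 0.75: r = 0.80, combined chance 7.4%
- k = 1: r = 0.71, combined chance 7.9%

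**Step 5: with CAL gated on PD in the same arm.** With no true effects, a false CAL finding can occur only after a false PD finding. The chance of any false finding is then that of PD alone, 4.65%. More generally, each arm's sequence is held at 0.025, so both arms together stay within 2 × 0.025 = 0.05 whichever effects are real.

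**Step 6: sensitivity to the all-null assumption.** If only one arm is without effect, the chance of a false PD or CAL finding in that arm is 4.95% (r = 0), 4.7% (0.5), 4.3% (0.7) or 3.6% (0.9), against 2.5% with gating.

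**The case against.** **No stated rule is broken.** It is tempting to infer that the SAP exceeds its own 5%. The documents do not support that. 8.3.1 corrects for the two primary hypotheses and 8.3.2 corrects separately for the two secondary comparisons; each set is held at 0.05, and neither document promises 5% across PD and CAL. This stands: 5% overall is a usual study-wide target, not the SAP's claim.

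**The size is not fixed.** A reader might also take a figure such as 7% to 9% as established. That range needs r between about 0.2 and 0.86, and the documents give no r. Since CAL contains probing depth and is analysed at the same tooth-sites on the same day, r = 0 is a limiting case rather than a likely one, and r above 0.86 is possible. This stands too.

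**Direction.** The counts include findings of harm. Counting only findings that favour ST266, the combined chance runs from 3.0% (r = 0.95) to 4.6% (r = 0), against 2.3% for PD alone. The absolute figures halve; the relative excess remains.

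**Silence is not permission.** The SAP nowhere says that CAL may be claimed after PD fails, so such an intention should not be read into it. But it spells out an order, a level and a gatekeeper, and following those words leads to testing CAL whatever PD shows. If gating was meant, the sentence is missing.

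**Context.** This is a Phase 2a study whose SAP states its purpose as estimation. A failed primary would be visible beside any CAL result, and CAL and BOP estimates with 95% confidence intervals are planned regardless. That limits the consequence without removing the ambiguity.

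**Conclusion.** The point holds as a gap in the testing scheme, not as an error in a stated figure. As written, SAP 8.3.2 allows a formal CAL claim in an arm where PD was not significant.

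The combined two-sided chance of a false PD or CAL finding is about 6% to 9%, at most 10%, against about 4.65% with gating. The lower half of that range is the more plausible, given how CAL is constructed, and the figure falls to 4.65% only as r approaches 1. These numbers assume that neither regimen affects either endpoint, that allocation is equal with a shared placebo arm, and that r takes the assumed values. The primary PD tests keep their stated level in every case. This is a low-priority but inexpensive improvement.

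**What to change.** In SAP 8.3.2, state that within each active arm testing runs PD, then CAL, then BOP, each at 0.025 against placebo, and stops at the first non-significant result. Endpoints after the stop are reported as estimates with confidence intervals, which 8.3.2 already plans.

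This takes one sentence and needs no additional subjects. The power of the PD tests and the CAL and BOP estimates do not change. The cost is that no formal CAL claim, and hence no BOP claim, can be made in an arm where PD is not significant. If the sponsor prefers to keep CAL ungated, the SAP should say so and state that error is controlled separately for the primary and secondary comparisons, not across them.
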